### **2.7.2 Statistical hypothesis, model, and method of analysis**

Not applicable.

### **2.7.3 Handling of missing values/censoring/discontinuations**

Missing values are not replaced.

## **2.8 Safety analyses**

All safety analyses are presented for the Safety Set (SAF). Descriptive statistics are presented within study treatment groups (cohorts 1-3).

It should be mentioned that the follow-up analysis amends all analyses of adverse events. The CSR is planned to be finalized after this follow-up analysis.

### **2.8.1 Adverse events (AEs)**

According to the CSP all adverse events starting in the on-treatment period, i. e. the treatment emergent AEs, are analyzed.

The on-treatment period lasts from the date of first administration of study treatment after informed consent to 30 days after the month 12 COVID-19 follow-up call.

The number (and percentage) of subjects with treatment-emergent adverse events will be summarized in the following ways:

- by treatment group (cohort 1-3), primary system organ class and preferred term.
- by treatment group (cohort 1-3), primary system organ class, preferred term and maximum severity

A subject with multiple AEs within a MedDRA primary system organ class is only counted once towards the total of the primary system organ class.

A subject with multiple AEs within a preferred term is only counted once towards the total of the preferred term class.

Separate summaries will be provided for study medication related AEs, death, SAEs, AEs leading to discontinuation and adverse events leading to dose adjustment.

The absolute and relative frequency of COVID-19 infections is presented.

Deaths and serious adverse events are listed in addition.

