- Participants in cohort 1: vaccination will be administered according to EU SmPC under continued siponimod treatment. In case of a booster vaccination, patients in this cohort may also undergo a treatment break which is also covered by the EU SmPC.
- Participants in cohort 2: vaccination will be administered according to EU SmPC after start of the siponimod treatment break.
- Participants in cohort 3: vaccination will be administered according to EU SmPC during continued treatment with first-line MS DMTs or no current treatment.

If suggested by local regulations, patients will be allowed to receive additional SARS-CoV-2 vaccinations (booster or refresher) during the study according to the physician's discretion and as part of the clinical routine. This booster may be any type of SARS-CoV-2 vaccine, depending on local regulations. According to SmPC, siponimod patients in Cohort 1 and Cohort 2 may introduce a treatment break for the purpose of the booster vaccination e.g. in case there was no measurable immune response during the initial vaccination cycle. The decision for such a treatment break is at the discretion of the treating physician and patient.

3. Investigational period

[figure not shown]
Blood samples for SARS-CoV-2 functional antibody titers and T-cells for primary and secondary endpoints will be drawn from all patients 1 week (day 6 - 10), 1 month (day 28 - 35)

and 6 months (week 25 - 27) after completion of vaccination. In case of booster vaccinations an additional blood sample will be collected one month (+/- 1 week after the booster vaccination).

12 months (week 50 – 54) after completion of the vaccination a COVID-19 follow-up call is scheduled to inquire about a possible confirmed COVID-19 disease after the end of the study.

In total, the study duration for each participant is 56-60 weeks, depending on the length of the screening period.

Figure 3-1 Study design

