It is unlikely that there will be a direct benefit to the patient as a result of the participation in this study other than receiving the information whether measurable SARS-CoV-2 antibody and T-cell levels are reached after the vaccination. This information can then be used to decide whether an additional booster vaccination might be necessary in MS patients with/without concomitant immunosuppressing/immunomodulating therapy. Furthermore, the results of the study will contribute to a better understanding of immune responses to modRNA vaccines in siponimod treated SPMS patients. Findings can inform physicians and patients if risk factor management may need to be reviewed and potentially give additional guidance for vaccination with the novel class of modRNA vaccines in MS patients.

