^QFurthermore, an additional study visit will be performed one month (+/- 1 week) after the booster vaccination matching all assessments of investigational visit 3. If this unscheduled visit falls within +/- 1 week of the regular visit 3 or later than the telephone contact in month 12, it will not be performed. * Number of required vaccinations and interval depends on the SmPC of the respective modRNA vaccination. ** Patients need to be sent into quarantine immediately in case of positive test results. Patients in this study are only allowed to continue the study and receive SARS-CoV-2 vaccination after they received a negative PCR test result. *** Required minimum of sensitivity of the pregnancy test is HCG 25 mIU/mL. **** MS relapses within the last two years should be recorded.

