## **2.4 Treatments (study treatment, rescue medication, concomitant therapies, compliance)**

### **2.4.1 Study treatment / compliance**

The absolute and relative frequency of performed study visits and performed vaccinations are presented. Sample statistics for the duration of intervals between screening and date of 1st vaccination, date of 1st and 2nd vaccination and date 2nd vaccination to Visit 1/Week 1 are displayed. The interval from the 2nd Vaccination to Visit 1/Week 1, Visit2 /Month 1 and Visit 3/Month 6 are also displayed by sample statistics. Here always the exact date of the respective vaccination is used but not the date of study visit called “Vaccination 1” or “Vaccination 2” which displays the date of phone contact with the patient.

Two types of investigational study drugs are used in this study:

1. Study medication for treatment of MS
2. Study medication for vaccination

The study medication for treatment of MS is displayed by frequencies for type of medication (cohort 3 only), sample statistics for duration of treatment prior to screening (cohort 1 and 3) and frequencies of dose changes, interruptions, or discontinuation until Visit 1, 2, and 3 respectively (cohort1 and 3). For cohort 2 the duration of siponimod interruption (i. e. the time between last dose prior to vaccination and the fist dose after vaccination) is displayed by sample statistics.

The different vaccines are displayed by a frequency table separately for 1st and 2nd vaccination.

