## 2.5.4 Supportive analyses

If relevant differences in demographic or other baseline characteristics are observed post-hoc analysis will be performed to adjust the primary endpoint for these inhomogeneities. A logistic regression model would be applied.

The qualitative and (semi)quantitative antibody results towards coronaviridae are analyzed in addition. The first by frequency tables, the latter by sample statistics.

In several patients the booster vaccination was performed before Visit 3 at Months 6, so that the efficacy results were expected to be influenced by this booster vaccination. Therefore, the analyses of seroconversion in SARS-CoV-2 functional antibodies and reactivity to IFNg and IL-2 SARS-CoV-2 were presented for both subgroup of patient who received / did not receive a booster vaccination before Visit 3 at Month 3.

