## **2.8.4 Other safety data**

### **2.8.4.1 Physical examination**

Clinically significant findings which were not present at screening but at any later visits are displayed by a frequency table.

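### SAP 2.8.1 does not separate adverse events after an optional booster from those of the two-dose cycle, so cohort AE percentages may partly reflect booster uptake

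*SAP*

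**What the plan says.** The AE period in SAP 2.8.1 "lasts from the date of first administration of study treatment after informed consent to 30 days after the month 12 COVID-19 follow-up call". Protocol 12.4.1 ends the period at the same point. Within it, subjects with events are counted "by treatment group (cohort 1-3), primary system organ class and preferred term", and again by maximum severity. Related AEs, SAEs, deaths and AEs leading to discontinuation or dose adjustment get separate summaries. None of these is split, censored or exposure-adjusted at a booster.

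Protocol section 3 (vaccination period) allows boosters under local rules and routine care: "This booster may be any type of SARS-CoV-2 vaccine, depending on local regulations". Patients in cohorts 1 and 2 may also pause siponimod for the booster. Table 8-1 adds a booster telephone contact, and its footnote states that "an additional study visit will be performed one month (+/- 1 week) after the booster vaccination matching all assessments of investigational visit 3". That visit is omitted if it falls within a week of Visit 3 or after the Month-12 call. The AE/SAE row is marked at both booster contacts.

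Protocol 4.5 says of the measured antibody and T-cell result: "This information can then be used to decide whether an additional booster vaccination might be necessary".

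SAP 2.5.4 recognises that boosters before Visit 3 could influence efficacy, so "the analyses of seroconversion in SARS-CoV-2 functional antibodies and reactivity to IFNg and IL-2 SARS-CoV-2 were presented for both subgroup" of patients with and without one. In SAP 2.4.1, "The different vaccines are displayed by a frequency table separately for" the first and second vaccination; the booster is not included. In SAP 2.8.4.1, "Clinically significant findings which were not present at screening but at any later visits are displayed by a frequency table", with no distinction between scheduled and booster visits.

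**The concern.** The AE endpoint is worded as continued siponimod versus treatment break versus first-line or no DMT, so readers will set the cohort percentages side by side. A boosted patient has one more dose that can cause a reaction and more occasions on which events are asked about. The measured vaccine response may guide the decision to boost, and response is what the trial studies by cohort. Booster use may therefore follow from cohort membership.

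If a cohort with weaker responses is boosted more often, it can show more AEs, more vaccine-related AEs and more new examination findings with no difference in risk per dose. The planned tables would not reveal this, because they show neither how many boosters were given in each cohort nor of which type. A cohort 1 patient who pauses siponimod for a booster also continues to contribute events to the continued-treatment column.

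**Working it through.** The plan states no figure for AE exposure or precision, so there is nothing of its own to reproduce here. The check counts from Protocol Table 8-1 and then illustrates the size.

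**Step 1: counts from Table 8-1, after screening.** The AE/SAE row has 9 marks. Removing screening and the two booster marks leaves 9 − 1 − 2 = 6 (two vaccination calls, Visits 1 to 3, Month-12 call).

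| | No booster | Booster, visit held | Booster, visit omitted |
|---|---|---|---|
| Vaccine doses | 2 | 3 | 3 |
| AE contacts | 6 | 8 (8/6 = 1.33) | 7 (7/6 = 1.17) |
| Post-vaccination full exams | 1 | 2 | 1 |

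The third dose and at least one extra contact apply to every boosted patient. The second extra contact and the extra full examination apply only if the booster visit takes place.

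**Step 2: effect of the extra dose on the percentage of subjects.** The SAP counts subjects, so the relevant quantity is the probability of at least one reaction. Assumptions, none from the documents: the same risk q per dose in every cohort, independent doses, and booster uptake u1 and u2 in two cohorts.

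- Two doses: P2 = 1 − (1 − q)². Three doses: P3 = 1 − (1 − q)³.
- P3 − P2 = q(1 − q)².
- Difference between cohorts = (u1 − u2) × q(1 − q)².

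| q | q(1 − q)² | Uptake 80% vs 40% (× 0.4) | Uptake 90% vs 30% (× 0.6) |
|---|---|---|---|
| 0.2 | 0.128 | 5.1 points | 7.7 points |
| 0.3 | 0.147 | 5.9 points | 8.8 points |
| 0.5 | 0.125 | 5.0 points | 7.5 points |

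With the planned 20 patients per cohort, 5.0 to 5.9 points is 1.0 to 1.2 patients, and 7.5 to 8.8 points is 1.5 to 1.8 patients. With equal uptake the difference is zero.

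**Step 3: sensitivity to independence.** If the same patients react at every dose, P2 = P3 = q and the difference is zero. Step 2 therefore overstates the effect to the extent that reactions cluster within patients.

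**Step 4: effect of extra contacts alone.** Let c be the chance of a report at each contact, taken as independent. With 8 versus 6 contacts, the difference is (u1 − u2) × [(1 − c)⁶ − (1 − c)⁸]. For an uptake gap of 40 points it is 2.9, 4.0 and 3.8 points at c = 0.05, 0.1 and 0.2. This is generous, since it assumes that every booster visit is held and that an event missed at one contact is not picked up later. It should not be added to Step 2.

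**The case against.** **The long period is intended.** The safety objective covers AEs of stopping and newly starting siponimod, and COVID-19, which needs follow-up to Month 12. A reader might infer that the safety endpoint concerns only the modRNA cycle and that post-booster events do not belong in it. The documents do not support this: the safety endpoint does not mention modRNA, and Table 6-1 lists vector vaccine as investigational in every cohort. This objection stands, and the whole-period tables should remain.

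**Unequal uptake is not shown.** Boosters follow local rules and routine care in all cohorts, and Protocol 4.5 leaves response-guided boosting open to patients with or without immunosuppressive or immunomodulating therapy. This stands. A difference in uptake is plausible, and the planned tables could not show whether it occurred.

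**Ascertainment is less unequal than the contact count suggests.** Calendar follow-up is the same, AEs carry start dates, and everyone is asked again at Month 12. This weakens the argument about contacts but leaves the third dose untouched.

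**The analysis is descriptive and non-randomised, and deaths and SAEs are listed individually.** No test is distorted, and serious events can be placed relative to a booster whose date is documented. Non-serious events appear only in pooled percentages, and those percentages are what readers will compare.

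**A common window from dose 1 to day 35 after dose 2 may look like the obvious remedy.** It would cut out part of the stated objective. The cohort 2 break begins before dose 1, and SAP 5.2 counts events from consent when the break starts after consent. The break lasts about 2 to 3 months. The label text quoted in Protocol 1.1 runs to 4 weeks after vaccination, so day 35 leaves 35 − 28 = 7 days after such a restart.

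**Conclusion.** The gap is real and moderate. The AE tables pool events before and after an optional booster, booster use is not tabulated by cohort, and the SAP allows for booster influence in efficacy only. Each boosted patient has a third dose and one or two more AE contacts, with a second post-vaccination full examination only when the booster visit is held.

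Under the assumed 80% versus 40% uptake, 20% to 50% risk per dose and independent doses, the artificial difference is about 5 to 6 points, or about one patient in 20. It shrinks towards zero if reactions cluster in the same patients or uptake is similar.

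A reader might infer that the cohort safety comparison is biased. The documents do not support that: they give no uptake by cohort. What they do show is that the planned tables could not distinguish a cohort difference from a difference in booster use.

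**What to change.** Keep the whole-period AE tables as the main safety tables. In SAP 2.8.1 add, by cohort:

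- **(a) Before the booster:** the SOC/PT, severity, related-AE and SAE tables for events from the SAP 5.2 start of the on-treatment period until the booster date or the start of a booster-related siponimod break, whichever is earlier, or the end of the period if neither occurs. Show patient-time, because this censoring makes follow-up unequal.
- **(b) After the booster:** a separate table of AEs with onset on or after that date.

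In SAP 2.4.1, tabulate booster number, vaccine type, timing and any booster-related siponimod break by cohort. In SAP 2.8.4.1, show new findings at Visits 1 to 3 separately from those found only at the booster visit, and flag Visit 3 findings made after a booster.

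The cost is SAP wording and one more set of tables. Booster type and date, AE start dates and MS medication status are already recorded; which breaks were for a booster would have to be settled at data review. The downside is small numbers after the booster.

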- *Vaccinations may be less effective if administered during siponimod treatment. Discontinuation of treatment 1 week prior to planned vaccination until 4 weeks after is recommended. When stopping siponimod therapy for vaccination, the possible return of disease activity should be considered*

The modRNA vaccine BNT162b2 was shown to not only trigger a vaccine-induced antibody response against the receptor binding domain (RBD) of the SARS-CoV-2 spike protein but also a functional and proinflammatory CD4+ and CD8+ T-cell response in a phase I/II trial (NCT04380701) (Sahin et al, 2020). In the following phase III trial with 43,548 participants (NCT04368728), BNT162b2 mRNA vaccine has further been shown to be 95% effective in

preventing COVID-19 (Polack et al, 2020). Similar results were also shown for the mRNA vaccine developed by Moderna: the efficacy of mRNA-1273 in preventing COVID-19 in a phase III trial with 30,420 participants was 94.1% (NCT04470427) (Lindsay et al, 2021).

It is therefore essential to understand the immune response to the novel class of modRNA vaccines in siponimod treated patients where S1P1 expressing Th17 cells are retained in lymph nodes (Behrangi et al, 2019) to develop a guidance for SARS-CoV-2 vaccination strategies in the vulnerable population of SPMS patients. This becomes even more important when considering that SARS-CoV-2 vaccination needs to be boosted after 3 or 4 weeks, resulting in a possible treatment interruption of about 2-3 months.

The detection of SARS-CoV-2 serum functional antibodies after vaccination in patients negative for this parameter at baseline is defined as seroconversion according to World Health Organization guidelines (WHO guideline, 2020). In this study, we will test for functional antibodies, i.e. antibodies that inhibit the binding of the viral spike protein to the human angiotensin-converting enzyme 2 (ACE2) receptor, which is the first and necessarily required step during SARS-CoV-2 infection (Yang et al, 2020). Vaccination response will be analyzed during continued siponimod treatment (cohort 1) or a short treatment interruption (cohort 2) in accordance with label recommendations / upon discretion of the treating physician to cover both scenarios taking place in clinical practice.

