### **Secondary Objective(s)**

- Describing SARS-CoV-2 serum functional antibody levels in participants treated concomitantly with siponimod versus siponimod treatment break versus first-line DMTs and in patients currently not on a DMT
- Describing the T-cell response to modRNA vaccines in participants treated concomitantly with siponimod versus siponimod treatment break versus first-line DMTs and in patients currently not on a DMT
- Describing safety, incl. AEs related to discontinuation and new onset of siponimod treatment and patients developing COVID-19

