### **Endpoint(s) for secondary objective(s)**

- SARS-CoV-2 serum functional antibody levels one week, one month and six months after second dose of vaccine in participants treated concomitantly with siponimod versus siponimod treatment break versus first-line DMTs and in patients currently not on a DMT
- SARS-CoV-2 specific T-cell levels one week, one month and six months after second dose of vaccine in participants treated concomitantly with siponimod versus siponimod treatment break versus first-line DMTs and in patients currently not on a DMT measured by e.g. enzyme-linked immunosorbent spot (ELIspot) assay from peripheral blood mononuclear cells that were stimulated with SARS-CoV-2 peptide mix
- AEs, SAEs, incl. patients with clinical confirmed COVID-19, events leading to discontinuation in participants treated concomitantly with siponimod versus siponimod treatment break versus first-line DMTs and in patients currently not on a DMT.

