## 2.7 Analysis of secondary efficacy objective(s)

### 2.7.1 Secondary endpoints

The secondary endpoints are analyzed descriptively within each cohort. The efficacy analysis set is used for all analyses of the secondary parameters.

The semiquantitative SARS-CoV-2 serum functional antibody titer (percent inhibition) is summarized by arithmetic mean, standard deviation, minimum, median and maximum by visit. A boxplot graph will be presented.

The SARS-CoV-2 serum functional antibody titer is summarized by geometric mean, geometric coefficient of variation (CV) and 95% confidence intervals for the (geometric) mean. The Visits Screening, Visit 1/Week 1, Visit 2 /Month 1 and Visit3 /Month 6 are displayed separately in this summary table and a boxplot graph with logarithmic y-axis (log base 10).

The same summary table and boxplot will be provided for the following secondary parameters:

- a) Qualitative and quantitative result of IFNg towards SARS-CoV-2 and towards coronaviridae
- b) Qualitative and quantitative result of IL-2 towards SARS-CoV-2 and towards coronaviridae
- c) Combined response in qualitative INFg or IL-s towards SARS-CoV-2 and towards coronaviridae, i. e. reactive to INFg or IL-2 or to both.
- d) Cell viability, CD3 lymphocytes, CD4 and CD8 cells, percentage of CD4+ and CD8+ cell in peripheral blood mononuclear cells

The percent inhibition values for INFg at screening will be displayed for the subset of patients who are reactive at Week 1 versus non-reactive. The same analysis is provided for IL-2.

All other laboratory data (e. g. number of basal/background spots, spots, quality, comments, mutations) are listed only.

The MS activity is measured by relapses. The crude annual relapse rate until end of study and underlying sums (of relapses and patient-years) will be presented.

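### AEs and relapses during the cohort 2 siponimod break and after restart are not shown separately, although a secondary objective asks about stopping and starting siponimod

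*SAP*

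**What the plan says.** The third secondary objective, in Protocol Table 2-1 and SAP 1.2, reads "Describing safety, incl. AEs related to discontinuation and new onset of siponimod treatment and patients developing COVID-19". The endpoint set against it is worded differently: "AEs, SAEs, incl. patients with clinical confirmed COVID-19, events leading to discontinuation in participants treated concomitantly with siponimod versus siponimod treatment break", with the contrast continuing to the cohort 3 groups.

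SAP 2.8.1 follows the endpoint. Treatment-emergent AEs are tabulated "by treatment group (cohort 1-3), primary system organ class and preferred term", and again with maximum severity, each subject counting once per class and once per term. The window opens at the first study treatment after consent and runs "to 30 days after the month 12 COVID-19 follow-up call". The additional outputs are these: "Separate summaries will be provided for study medication related AEs, death, SAEs, AEs leading to discontinuation and adverse events leading to dose adjustment". AEs of special interest (2.8.1.1) cover COVID-19 only.

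For relapses, SAP 2.7.1 says: "The crude annual relapse rate until end of study and underlying sums (of relapses and patient-years) will be presented".

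The break appears in one planned output. SAP 2.4.1 gives sample statistics: "For cohort 2 the duration of siponimod interruption", measured between the doses on either side of vaccination. Protocol section 3 puts its length at about 2-3 months. Protocol 1.1, citing the product label, warns: "When stopping siponimod therapy for vaccination, the possible return of disease activity should be considered".

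**The concern.** The objective and the outputs point in opposite directions. The objective concerns events that follow stopping or starting siponimod; the table of AEs leading to discontinuation concerns events that bring stopping about. In cohort 2 the drug is stopped for vaccination, so that table cannot describe what the break does.

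The protocol treats return of disease activity as the cost of a break and gives it as a reason not to randomise (Protocol 4.1). The study is meant to inform the choice between continuing and interrupting. As planned, it reports the immune response around the break but gives no separate account of safety in that time. Events in a short period off drug, or just after restart, are merged with the rest of a follow-up that is mostly on drug. Cohort 1 patients, who may pause siponimod for a booster (Protocol 3 and 6.1.3), raise the same gap.

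**Working it through.** **1. Does any planned output answer the objective?**
- AE tables by cohort, class, term and severity (SAP 2.8.1): they include break time but have no period split. A term reported both inside and outside the break counts once.
- AEs leading to discontinuation or dose adjustment: the reverse relation.
- Medication-related AEs: may contain restart reactions, but do not time or identify them. SAP 2.1.1 makes both the vaccine and the MS drug study treatments.
- Listings of deaths and SAEs: individual events, but non-serious AEs are not covered.
- Analyses at Week 1, Month 6 and Month 12 (SAP 1.1): cut by study visit, not by siponimod status.
- Break duration (SAP 2.4.1): no events.
- Subgroups: none under SAP 2.2.1; the booster split in 2.5.4 covers immune response only.

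None separates the break or the restart.

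**2. Length of follow-up.** Protocol section 3 states 56-60 weeks. The components in the Amendment 1 summary reproduce this: 1 + 3 + 52 = 56 and 4 + 4 + 52 = 60 weeks. The AE window adds 30 days: 56 x 7 + 30 = 422 to 60 x 7 + 30 = 450 days, or 60.3-64.3 weeks.

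**3. Share of the relapse period spent in the break.** One month is 365.25/(12 x 7) = 4.35 weeks, so 2-3 months is 8.70-13.04 weeks. The relapse rate runs to end of study, so the denominator is 56-60 weeks (assumed to start at screening). The share f is 8.70/60 = 14.5% to 13.04/56 = 23.3%.

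**4. Dilution of a relapse excess.** If the rate in the break is k times the rate outside it, then pooled rate / rate outside = 1 + f(k - 1). The documents give no k; these values are assumptions.

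| k | f = 14.5% | f = 23.3% |
|---|---|---|
| 2 | 1.145 | 1.233 |
| 3 | 1.29 | 1.47 |
| 5 | 1.58 | 1.93 |

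This is a formula for rates. The AE tables count subjects, so it does not describe them.

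**5. Illustration.** Take 22 patients, 58 weeks and a 2.5-month break. Total time is 22 x 58 x 7/365.25 = 24.5 patient-years; break time is 22 x 2.5/12 = 4.58. Four relapses give 4/24.5 = 0.16 per year wherever they fall. If all four fall in the break, the rate there is 4/4.58 = 0.87 per year and zero elsewhere. The planned output cannot tell these cases apart.

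**6. What a split would hold.** Break time is 20 x 2/12 = 3.3 to 22 x 3/12 = 5.5 patient-years, out of 20 x 56 x 7/365.25 = 21.5 to 22 x 60 x 7/365.25 = 25.3.

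**7. Effect of the treatment-emergent rule.** Under SAP 5.2, if a cohort 2 patient stopped siponimod before consent, the AE window opens at first vaccination or at an earlier siponimod dose. With consent at screening, 3-30 days before vaccination (Table 8-1), up to 30 days of observed break time are dropped from the AE tables rather than pooled. That is at most 30/60.9 = 49% of a 2-month break. Inclusion criterion 4 asks for no interruption in the 4 weeks before inclusion, so such patients may be few, but SAP 5.2 provides for them.

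**The case against.** The SAP implements the endpoint as the protocol defines it; the mismatch with the objective begins in Protocol Table 2-1. Cohort 2 against cohort 1 over the whole period does describe the two strategies a physician chooses between. Break duration is summarised, SAEs and deaths are listed, and there are staged analyses as well as the final one. With 20-22 patients, period tables by class and term would be mostly zeros and ones.

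All of that is true, and it limits the point. It does not close the gap: a whole-period contrast of strategies is a different question from what happens on stopping and restarting, and no listed output carries timing relative to siponimod doses. Sparse counts argue for a simple format, not for omission.

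Three stronger readings are tempting and are not supported:
- A reader might infer that the break is invisible in the plan. It is not: its duration is reported, and events within it generally enter the pooled tables.
- A reader might apply the dilution factors to the AE tables. Those count each subject once, so the factors do not carry over.
- A reader might infer that cohort 2 will look as safe as cohort 1. Pooling shrinks the ratio, not the number of excess events; every relapse in the break still counts in cohort 2, and the documents give no event rates from which to predict the contrast.

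**Conclusion.** The point holds in this form: a stated secondary objective has no matching analysis, because AEs and relapses in the cohort 2 break and after restart are not shown separately. The gap lies in the protocol's endpoint and in SAP 2.7.1 and 2.8.1 alike. For relapses, an assumed 3-fold rate in the break would appear as about 1.29-1.47 fold in the pooled rate, and a 5-fold rate as 1.58-1.93. This rests on a 2-3 month break lying wholly within 56-60 weeks of follow-up, a constant rate outside it and no booster break.

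New onset is read here as restart. The documents do not define it, but enrolled siponimod patients must already be stable on the drug. The primary endpoint is untouched. The change should be made because the objective is the trial's own and the dosing dates are already needed for the interruption summary.

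**What to change.** In SAP 2.8.1 and 2.7.1, keep the pooled tables and add for cohort 2:
- Simple counts of subjects and events, with patient-time, for AEs and relapses by period: the break (last siponimod dose before vaccination to first dose after), a window after restart whose length the SAP states and justifies, and remaining time. State how patients with no restart are handled.
- Start both events and patient-time at the later of informed consent and last dose, and count all AEs after consent. Otherwise the rule in SAP 5.2 drops break events before first vaccination while their time is counted.
- A listing of AEs and relapses with onset relative to the last and first siponimod doses.

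Treat booster breaks in cohorts 1 and 2 the same way. If cohort 1 is shown as a reference, use one vaccination-anchored window applied identically to both cohorts and report rates per patient-time. A span from 1 week before dose 1 to 4 weeks after dose 2, with doses 3-4 weeks apart, is 8-9 weeks and does not match an 8.7-13.0 week break.

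Check the relapse denominator as well: as read from the PDF, Table 8-1 shows no relapse entry at the Month 12 call, while the rate runs to end of study. The table may be broken in extraction.

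The cost is SAP wording and a few tables and a listing from dosing and AE dates already recorded; relapse onset dates are assumed to be on the eCRF. Counts will be small, on about 3.3-5.5 break patient-years, which is acceptable in a descriptive study. The SAP's latest history entry follows the final data review, so the outputs should be labelled as added after it.
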